## 6 General Considerations and Statistical Issues

### 6.1 Timeline

1. Data Available: February 24, 2022
2. Analysis Done: April 20, 2022
3. Manuscript Complete: TBD

Table 11: Estimated difference in proportion of protective PrEP use between treatment groups and SOC group, where P3 and P3+ are considered separately (table 3)

P3 vs. SOC	Estimated Difference	95% CI
Protective PrEP Level in Blood: TFV-dp		
3 months		
6 months		
P3+ vs. SOC	Estimated Difference	95% CI
Protective PrEP Level in Blood: TFV-dp		
3 months		
6 months		
P3 vs. SOC	Estimated Difference	95% CI
Protective PrEP Level in Blood: FTC-tp		
3 months		
6 months		
P3+ vs. SOC	Estimated Difference	95% CI
Protective PrEP Level in Blood: FTC-tp		
3 months		
6 months		

Table 12: Estimated difference in self-reported PrEP use between treatment groups and SOC group.

P3/P3+ vs SOC	Estimated Ratio	95% CI	p-value
Self-reported Weekly PrEP Use			
3 months			
6 months			
Self-reported Monthly PrEP Use			
3 months			
6 months			
P3 vs SOC	Estimated Ratio	95% CI	
Self-reported Weekly PrEP Use			
3 months			
6 months			
Self-reported Monthly PrEP Use			
3 months			
6 months			
P3+ vs SOC	Estimated Ratio	95% CI	
Self-reported Weekly PrEP Use			
3 months			
6 months			
Self-reported Monthly PrEP Use			
3 months			
6 months			

Table 13: Estimated difference in proportions (or mean outcomes) between treatment group and SOC group for self-reported exploratory outcomes (table 5)

P3/P3+ vs SOC	Estimated Difference	95% CI	p-value
Outcome 1			
3 months			
6 months			
Outcome 2			
3 months			
6 months			

Table 14: Frequency of Missing Data, in entire cohort and by treatment group, reported as count (%). (table 7)

Variable	Total (N= )	P3 (N= )	P3+ (N= )	SOC (N= )
Baseline data				
Baseline Variables				
3 month data				
TFV-dp				
FTC-tp				
Outcome 1				
...				
Outcome p				
6 month data				
TFV-dp				
FTC-tp				
Outcome 1				
...				
Outcome p				

## 6.2 Missing Data and Modification of Primary Analysis

Due to COVID-19, the collection of dry blood spots (DBS) was interrupted during this study. Therefore, the missingness in DBS will be high and it is possible for patients to have follow-up survey data, while missing the DBS follow-up data, or vice versa. Although TMLE can accommodate missingness at random (conditioned on baseline covariates) in the outcome of interest, a high amount of missing data in DBS will increase the variance of the estimator. Therefore, we decided to use survey data to “impute” the outcome variable. In doing so, we also require additional regression models to build the estimator for ATE. Please refer to the Supplement for details.

There are two survey variables that will be used to impute the values of the DBS data, namely PrEP use in the past week (number of days) and PrEP use in the past month (reported as a percentage of days). If the patient reported that they are *not* currently on PrEP, then the weekly PrEP use is assumed to be zero.

It is possible for one survey question to be present, but the other to be missing. In these cases we will use three simple forms of imputation to deal with the missing survey variable:

1. We will use mean imputation. First we stratify by current PrEP use (Y/N) and then within each group we perform mean imputation for the missing variable.
2. We will predict the survey variable (weekly or monthly PrEP use) with the other survey variable that is present using simple linear regression models
3. To impute weekly PrEP use from monthly PrEP use, we scaled the participant’s month variable to range from 0-7. Similarly to impute monthly PrEP use from weekly PrEP use, we scaled the participant’s week variable to range from 0-100.

Once this imputation is performed we can build a super learner library that includes each of the imputation methods and allow the super learner to pick the “best” methods via giving them weight in the final learner.

In addition to missingness in DBS and survey data, there may be missingness in other baseline measures or follow-up data of interest. We will assess the data for missingness in other data points and report the frequency of missing data points (see shell table 14). The method for handling missing values will be determined once the severity of missingness is understood and after discussion with the research team to understand potential causes for the missing data. Options for handling this missing data include imputation or omitting the follow-up data for a patient (i.e. consider setting  $\Delta_{Y,ij} = 0$  for the patient).

### 6.3 Confounder Selection

Since treatment was randomized in this study, our primary concern is controlling for confounders that affect both whether patients remain in the study and whether patients adhere to PrEP.  $W_0$  and  $W_1$  are potentially high-dimensional vectors, therefore, it is best advised to select a subset of the covariates to control for in the analyses. Factors identified by the study team that predict PrEP adherence are: age, race/ethnicity, PrEP stigma, substance use, mental health, prior PrEP use, PrEP self-efficacy, partner serostatus, and sexual behavior. In the interest of parsimony, we selected age, baseline DBS, site, race/ethnicity, and baseline PrEP use (yes/no) as the variables to control for in our analysis.

It is possible that there are time-varying confounders of the missingness/outcome relationship. Unfortunately, we cannot account for these confounders for our analysis of the three month time point. For the six month outcome, a confounder of the missingness/outcome relationship may be PrEP use at three months. One assumption of our primary analysis, is that this confounding does not exist or is negligible.

### 6.4 Definition of the Primary Outcome

To better understand the sensitivity of our primary analysis to how adherence to PrEP was measured, we also considered alternative definitions of adherence as a sensitivity analysis. The alternative definitions considered were *both* TFV-dp and FTC-tp levels in the blood consistent with PrEP use  $> 4$  days per week and *at least one* blood marker, TFV-dp for FTC-tp, consistent with PrEP use  $> 4$  days per week.

## A Supplement

### A.1 G-Formula for causal estimands of interest

The g-formula allows us to estimate our causal estimands with the observed data (under assumptions). For the counterfactual outcomes under treatment  $a_k$ ,  $E[Y_j(a_k)]$ , where  $j=1,2$ , we may define the following quantities:

- $Q_1^j(y, w_0)$ : the conditional CDF of  $Y_j$  given  $A = a_k$ ,  $\Delta_{Y,j} = 1$ , and  $W_0$
- $Q_0^j(w_0)$ : the CDF of  $W_0$ .

With these CDFs, we may define the g-formula as:

$$E[Y_j(a_k)] = \int \bar{Q}_1^j(w_0) dQ_0^j(w_0)$$

where

$$\bar{Q}_1^j(w_0) = \int y dQ_1^j(y, w_0)$$

### A.2 Causal Assumptions

In order to establish identifiability of the expected counterfactual outcomes via the g-formula written above, a few assumptions are necessary. We assume randomization which states that  $A \perp\!\!\!\perp Y(a) | W_0$  and also that  $\Delta_{Y,j} \perp\!\!\!\perp Y(a) | W_0, A$ . We know that the first randomization assumption holds because treatment was randomized in this study. For the second randomization assumption to be true, we assume that we have controlled for all confounders of missingness and outcome relationship via the baseline variables controlled for in our analyses (age, On PreP, and outcome of interest measured at baseline). This assumption also implies that there is no time varying confounding, or variables after baseline which affect the relationship between missingness and the outcome.

The second major assumption is the positivity assumption, which states that  $P(A = a | W_0) > 0$  for all  $a$  and  $P(\Delta_{Y,j} = 1 | W_0, A) > 0$ . This assumption states that each participant has a non-zero probability of receiving treatment  $a$  (which is true since this is a randomized trial), and a non-zero probability of having data for each follow-up time point, given treatment and baseline covariates. The last major assumption is the consistency assumption which states that for a patient whose treatment  $A = a$ , the outcome we observe is equal to the counterfactual outcome under treatment regimen  $a$  for that patient.

### A.3 Super Learning and TMLE Parameters

Certain parameters should be specified a priori for using the super learner and TMLE. For both the outcome regression and the propensity for missingness we will use 10-fold cross validation. The "method" used will be CC\_nloglik for binary outcomes and CC\_LS for continuous outcomes. These methods minimize the negative binomial log likelihood on the logistic scale and the squared error loss, for binary and continuous outcomes respectively. The appropriate "family" argument will also be specified according to the distribution of the outcome.

### A.4 Variance Estimation

We will obtain the influence curve for our estimators of interest, evaluated at each observation. This will allow us estimate the variance.

For example, let  $IC_{j1}(O_i)$  and  $IC_{j2}(O_i)$  denote the influence curve evaluated on observation  $i$ , for our estimator of  $E[Y_j(a_{k1})]$  and  $E[Y_j(a_{k2})]$ , respectively. We know that the distribution for our estimators of  $E[Y_j(a_{k2}) - Y_j(a_{k1})]$  under the null hypothesis of no difference between treatment groups, will be normal with mean zero and variance  $\sigma_j^2$ , where:

$$\sigma_j^2 = \text{Var}((IC_{j1}(O_i) - IC_{j2}(O_i)))$$

which may be estimated by:

$$\hat{\sigma}_j^2 = \frac{1}{n} \sum_{i=1}^n (IC_{j1}(O_i) - IC_{j2}(O_i))^2$$

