10.3.3 RCT Primary Analysis Plan

Primary Outcome: The primary analyses will assess the efficacy of the P3/P3+ intervention at 3- and 6-month follow-ups. Efficacy is defined in two ways (1) as the difference in the proportion of patients with protective levels of TFV-DP or TAF and (2) as the difference in the proportion of patients

with protective levels of FTC-TP, comparing the intervention arms to SOC. The primary tests of efficacy of the intervention (P3/P3+) will be of the following null hypotheses:

- (A1) There is no difference in the proportion of patients with protective levels of TFV-DP/TAF at 3 months.
- (A2) There is no difference in the proportion of patients with protective levels of FTC-TP at 3 months.
- (B1) There is no difference in the proportion of patients with protective levels of TFV-DP/TAF at 6 months.
- (B2) There is no difference in the proportion of patients with protective levels of FTC-TP at 6 months.

All hypotheses will be tested against the two-sided alternative of some difference in proportion. Each test will be conducted at the 0.05 level of significance and we will present corresponding 95% confidence intervals for the treatment effects.

For this analysis, we will use targeted minimum loss-based estimation (TMLE) to estimate the proportion of participants with protective levels of TFV-DP/TAF and protective levels of FTC-TP at each time and in each intervention group. TMLE is a methodology for constructing efficient and robust estimates of treatment effects and utilizes patient characteristics to account for bias due to informative participant dropout. If patient characteristics predict adherence, TMLE may also lead to greater power of tests about estimated treatment effects. Patient characteristics that will be considered in the estimation include demographic characteristics, social support, app usage and engagement, app acceptability, substance use, anxiety, and depression. We will use influence function-based variance estimators for the three- and six-month treatment effects to conduct Wald-style tests of the null hypotheses and to construct 95% confidence intervals.

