## 4.2 TMLE Analysis for Average Causal Effects

TMLE, combined with super learning, will be used to address both the primary and secondary study objectives. The regression models needed for TMLE estimation include the propensity for treatment, the propensity for missingness, and the outcome regression. We will use super learning to estimate these regressions. Super learning is a machine learning method that, when given a set of modeling algorithms, uses cross-validation to determine the optimal convex combination of the algorithms. This allows us to combine flexible learners with more traditional methods (linear/logistic regression) to create our models, and thereby improves the chances that the models are specified correctly. The details for building each regression are given below.

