### 4.3 Hypothesis Tests and Multiple Testing Adjustment

Table 8 lists the hypotheses to be tested for each study objective. Each hypothesis comparing P3/P3+ to SOC will be tested at both 3 and 6 months, separately. For comparisons of P3 vs SOC and P3+ vs SOC, we will report the comparisons in a descriptive manner as opposed to conducting additional hypothesis tests (i.e. Secondary objectives I, II, and III).

Table 8 lists the p-value adjustment for each hypothesis test. For the primary objective no adjustment is done. For secondary objective II, a Bonferroni Correction will be applied to adjust for multiple testing and to maintain a nominal alpha level of approximately 0.05 within the objective. Due to the exploratory nature of secondary objective III, we will use a Benjamini-Hochberg adjustment, which controls the false discovery rate (FDR). We will use 0.20 as the desired FDR, which is the proportion of rejected null hypotheses that are actually true (See Glickman, 2014 for more information).

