7. Fluctuate  $\bar{Q}_{a,n}(W, \delta)$  to get  $\bar{Q}_{a,n}^*(W, \delta, \epsilon)$  by fitting two logistic regression models for each possible treatment  $A = a$ . Both logistic regression models will use  $\tilde{Y}$  as the outcome, but different mean models (a) and (b) below.

- $\text{logit}(\bar{Q}_{a,n}(W, \delta = 1)) + \epsilon_1 \Delta_Y I(A = a) \frac{1 - \tilde{P}(\Delta_S = 1, \Delta_Y = 0 | W)}{\tilde{P}(\Delta_Y = 1, A = a | W)}$
- $\text{logit}(\bar{Q}_{a,n}(W, \delta = 0)) + \epsilon_2 \Delta_S I(A = a) \frac{\tilde{P}(\Delta_S = 1, \Delta_Y = 0 | W)}{\tilde{P}(\Delta_S = 1, A = a | W)}$

8. For those with  $\Delta_S = 1$  and  $\Delta_Y = 0$ , model (b) defines  $\bar{Q}_{a,n}^*(W, \delta, \epsilon)$ . Estimate  $\bar{Q}_{a,n}^*(W, \delta, \epsilon)$  with fluctuation (b) for these individuals under  $\Delta_S = 1$  and  $A = a$  for the participant.

9. For everyone not included in step 8 fluctuation (a) defines  $\bar{Q}_{a,n}^*(W, \delta, \epsilon)$ . Estimate  $\bar{Q}_{a,n}^*(W, \delta, \epsilon)$  with fluctuation (a) setting  $\Delta_Y = 1$  and  $A = a$  for the participant.

10. Take the sample mean of  $\bar{Q}_{a,n}^*(W, \delta, \epsilon)$  to estimate  $E[Y(a)]$ .

11. Calculate the treatment effect of interest in the analysis, as detailed in table 6.

12. The variance of the estimator for  $E[Y(a)]$  may be estimated with the sample variance of the efficient influence curve.

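### The primary standard errors come from influence curves that are not cross-fitted; if 40–50% of blood outcomes are missing, each nominal 0.05 test runs at about 7–9%

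*SAP*

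**What the plan says.** Protocol 10.3.3 sets four primary hypotheses (two markers, at 3 and 6 months): "All hypotheses will be tested against the two-sided alternative of some difference in proportion". It adds: "Each test will be conducted at the 0.05 level of significance". SAP 4.3 confirms there is no multiplicity correction: "For the primary objective no adjustment is done". The SE is specified in three places:

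- Protocol 10.3.3: "We will use influence function-based variance estimators for the three- and six-month treatment effects to conduct Wald-style tests of the null hypotheses".
- SAP A.4: "We will obtain the influence curve for our estimators of interest, evaluated at each observation".
- SAP A.5.4 step 12, for the survey-augmented estimator that serves as the primary analysis: the variance "may be estimated with the sample variance of the efficient influence curve".

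SAP A.3 mentions cross-validation: "For both the outcome regression and the propensity for missingness we will use 10-fold cross validation". SAP 4.2 explains what it is for: super learner "uses cross-validation to determine the optimal convex combination of the algorithms". It chooses learner weights. Neither section says that a participant's prediction comes from models that left that participant out. The only bootstrap in the SAP is for the cost ratio (4.4).

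SAP 6.2 expects high blood-spot missingness because of COVID-19 but gives no figure.

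**The concern.** Super learner normally uses its folds to set weights and then refits each learner on all available data. The influence curve contains the residual of each observed outcome from its own fitted value. When many coefficients are fitted to few outcomes, those residuals are smaller than they would be for new participants, and the variance is understated.

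The models are large for the data. The fullest GLM in SAP Table 15 has an intercept, two treatment terms, age, baseline DBS, baseline PrEP use, eight site terms (nine cities), one DBS-by-PrEP interaction and two age-by-treatment interactions. That is 1+2+1+1+1+8+1+2 = 17 coefficients, counting DBS as one variable and before race/ethnicity or the survey variables. With half the blood missing there are 120 observed outcomes. At the protocol's 27% adherence, about 0.27 × 120 = 32 of them are adherent.

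Every primary p-value and 95% interval rests on this SE. If it is too small, a true null is rejected more than 5% of the time, and a borderline result could be declared significant for that reason alone.

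**Working it through.** **The plan's own figures.** Protocol 10.2.3: 240 × (1 − 0.20) = 192, or 64 per arm, as stated. The protocol's data mechanism with influence-curve Wald tests (4,000 runs, joint two-degree-of-freedom test) gave 80.5% and 83.1% power for a 20-point effect at one time point only, which agrees with the stated >80%. The statement about effects above 14 points at both times did not reproduce (66% joint); that is a separate question. The text gives no figure for SE accuracy or type I error. Its power simulation uses one binary baseline covariate and 5% censoring per interval. With 200 data sets, the Monte Carlo SE of a 5% rate is √(0.05 × 0.95/200) = 1.5 points.

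**Inputs.** n = 240, 1:1:1 allocation, nine sites, no true effect and two-sided 0.05 (documents). Blood missingness of 5–50% and covariate strength are assumptions. A.4 as printed does not divide the variance by n; this is read as an omission and is not part of this point.

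**Measures.** The first is the ratio of mean SE to the empirical SD of the estimate. The second is size, the share of null trials with |estimate|/SE > 1.96. The Monte Carlo SE of a size is √[p(1−p)/R]: 0.35 points for 8.0% in 6,000 runs, 0.75 for 7.2% in 1,200 and 0.92 for 8.4% in 900.

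**Null simulations.** A and C used reduced learner libraries (A omitted HAL and step). B used analogues of the full library, because the R packages were not available. Paired values in B are with and without predictive covariates. B's 40% rows used an outcome intercept of 0 (50% adherence); its other rows used −1 (27%).

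| Estimator and simulation | Runs | Blood missing | In-sample SE/SD | In-sample size | Out-of-fold SE/SD | Out-of-fold size |
|---|---|---|---|---|---|---|
| Plain TMLE, A | 6,000 | 21% | 0.95 | 6.7% | – | 5.3% |
| Plain TMLE, A | 6,000 | 41% | 0.91 | 8.0% | – | 5.0% |
| Plain TMLE, A | 6,000 | 50% | 0.89 | 8.6% | – | 5.1% |
| Plain TMLE, B | 1,200 | 5% | 0.96, 0.98 | 6.9%, 5.3% | 1.00, 0.99 | 6.0%, 5.0% |
| Plain TMLE, B | 1,200 | 20% | 0.98, 0.99 | 5.9%, 5.2% | 1.03, 1.00 | 4.5%, 5.1% |
| Plain TMLE, B | 1,200 | 40% | 0.93 | 7.2% | 1.00 | 4.9% |
| Plain TMLE, B | 1,200 | 50% | 0.92 | 7.2% | 1.01 | 4.8% |
| Plain TMLE, C | 1,200 | about 20% | 0.96 | 5.5% | 1.00 | 4.8% |
| Plain TMLE, C | 1,200 | about 45% | 0.90 | 8.4% | 0.99 | 5.3% |
| A.5.4 steps, B | 900 | 40% | 0.94 | 7.3% | not run | not run |
| A.5.4 steps, B | 900 | 50% | 0.92, 0.92 | 8.4%, 7.4% | not run | not run |
| A.5.4 steps, one penalised main-effects model, A | 2,500 | 40% | – | 7.6% | – | 5.5% |
| A.5.4 steps, one penalised main-effects model, A | 1,500 | 50% | – | 8.3% | – | 5.2% |

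(A dash means not reported.)

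**Cross-check.** If only the SE were wrong, size = 2 × [1 − Φ(1.96 × ratio)]. A ratio of 0.94 gives 6.5% and 0.89 gives 8.1%. The simulated 7–9% is slightly higher, as can happen when the SE itself varies between trials. The simulated rates are the direct evidence.

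**Is it the simulation design, or super learner?** Unadjusted Wald tests on B's data had size 4.4–6.1%, so the design is not the source. A single main-effects GLM on the same data was no better: SE 5–14% too small, size 6.8–10.7%. Super learner is therefore not the specific cause. Out-of-fold evaluation hardly moved the ratio in those GLM runs (0.856 to 0.865 at 50% missing), so they show that the shortfall is not peculiar to super learner but do not demonstrate the repair.

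**The case against.** The strongest reply is that the size of the error rests on a percentage the documents do not give. That stands. A reader might infer that any trial of 240 analysed this way tests at 7–9%. The documents do not support that: at the planned 192 analysed (20% missing), sizes were 5.2–6.7%.

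A reader might also blame super learner. The GLM results contradict this. The SAP also took steps against overfitting: its revision history records adding a simple model and regularised learners because of the number of confounders, and section 6.3 cuts the covariate set for parsimony. Those steps help the fits but leave the SE calculation unchanged.

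That predictions are in-sample is an inference: the SAP does not say which predictions enter the influence curve. It is the natural reading of A.3 with section 4.2, and at the least the step is unspecified.

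A further reading would extend the fault to SAP Tables 11–13. This is not shown. Table 11 is descriptive, the others report survey outcomes whose missingness may differ, and none was simulated.

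Finally, SAP 6.1 dates the analysis as done on 20 April 2022, so changing the primary SE now is post hoc. That governs how the change is labelled, not whether the SE is right.

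**Conclusion.** The concern holds, conditionally on missingness. The primary SEs carry no protection against in-sample fitting, and the error runs in the anti-conservative direction.

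- **40–50% of blood missing at n = 240:** SE about 6–11% too small, size about 7–9%, so nominal 95% intervals cover about 91–93% under the null.
- **5–20% missing:** SE about 1–5% too small, size about 5–7%.

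The driver is the number of fitted terms (nine sites, race/ethnicity, interactions) relative to observed blood outcomes. The figures rest on assumed missingness and covariate strength and on approximations to the SAP's library. The out-of-fold repair was shown for plain TMLE with super learner and for A.5.4 with one penalised model, but not for A.5.4 with the full library.

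**What to change.** For the primary results (SAP Table 10), amend A.3, A.4 and A.5.4 step 12. Each participant's outcome, blood-missingness and survey-missingness predictions should come from models fitted without that participant. This must carry through the sequential A.5.4 models, because step 6 regresses a pseudo-outcome built in steps 1–5. Compute the influence curve from those predictions and base the 95% intervals and p-values on that SE.

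Label this as a dated change made after the analysis, and show the in-sample SE beside it. Give the observed blood missingness by marker and visit (already planned in Table 14) next to Table 10, so a reader can place the trial in the ranges above. Using the same SE for Tables 11–13 is optional.

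The cost is SAP wording, some programming for the sequential models and a rerun; no new data are needed. At high missingness the intervals widen by roughly 6–12% (1/0.94 = 1.06 to 1/0.89 = 1.12). In simulation C the spread of the estimate itself hardly changed.

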10.2.3 RCT Power Considerations

[figure not shown]
A total of 240 participants will be enrolled at baseline to account for a 20% expected loss to follow-up during the first 3 months of the study leaving an estimated 192 individuals (64 per arm) for analysis. Power was assessed via Monte Carlo simulation. Data were simulated as follows. A single binary baseline variable W was drawn from a Bernoulli (1/2) distribution to represent patient-level characteristics included in the analysis. A binary intervention variable A was drawn from a Bernoulli (2/3) distribution to mimic the 1:1:1 treatment allocation. A binary intermediate variable I_1 was drawn from a Bernoulli (3/4) distribution to mimic participant app utilization. A censoring variable C_1 for the month three visit was drawn from a Bernoulli (1/20) distribution, with the value 1 indicating a participant was lost-to-follow-up before the three-month visit. For uncensored participants, PrEP adherence at month three Y_1 was drawn from a Bernoulli distribution with adherence probability equal to $\text{logit}^{-1}(-1 + \beta_1 A)$. Thus, approximately 27% of participants in the SOC arm were assumed to be adherent at the three-month visit. Note that the parameter β_1 describes the log-odds-ratio of adherence comparing treatment to SOC. Next, we drew L_2 from a Bernoulli (3/4) distribution to mimic participant app utilization after the three month visit, and drew C_2 from a Bernoulli (1/20) distribution, where again a value of 1 indicated a participant was lost-to-follow-up between the three- and six-month visit. For uncensored participants, PrEP adherence at month six Y_2 was drawn from a Bernoulli distribution with adherence probability equal to $\text{logit}^{-1}(-1.5 + \beta_2 A + 1.5 Y_1)$. Thus, approximately 18% of participants in the SOC arm who were not adherent at month three, were adherent at month six, while 50% of participants in the SOC arm who were adherent at month three were again adherent at month six. Note that the parameter β_2 describes the log-odds-ratio of adherence at month six comparing treatment versus control for participants with the same month three adherence.

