We generated 200 simulated data sets of 240 participants from this mechanism and analyzed each data set using longitudinal targeted minimum loss-based estimation (TMLE). This process was repeated across a range of values for (β_1, β_2) . Results for our analysis are shown in Figure 1. This figure shows power (thick black lines) as a function of (β_1, β_2) . Because the analysis is not conducted on the odds ratio scale, we have also included grid lines (gray) for the corresponding risk differences. The vertical grid lines are labeled with the value of the difference in proportion of adherent participants (P3/P3+ versus control) at month three corresponding to the particular value of β_1 . The horizontal grid lines are labeled with the value of the difference in proportion of adherent participants at month six. From the figure, we may conclude that the study has >80% power to detect a six-month treatment effect of 20% (difference in percentage adherence) even if there is no three-month effect, or conversely a

three-month treatment effect of 20% even if there is no six-month effect. In the more realistic scenario, where there is a treatment effect at both time points, we have >80% power to detect effects if the three- and six-month treatment effects are >14%.

Though the baseline and interim participant characteristics were not predictive of adherence nor of censoring, we included these characteristics in the requisite regression models for TMLE. Thus, we expect that these power calculations will be conservative for the true power if participant characteristics are informative of adherence.

Figure 1: Power as function of 3-month and 6-month adherence

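### The SAP's influence-curve variance formulas omit division by n, so standard errors as written are √n too large (15.5-fold at n = 240)

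*SAP*

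**What the plan says.** SAP A.4 lets `IC_j1(O_i)` and `IC_j2(O_i)` "denote the influence curve evaluated on observation" i, one value per participant. It then says that the estimator of the treatment difference, "under the null hypothesis of no difference between treatment groups, will be normal with mean zero and variance" `σ_j²`. It defines `σ_j²` as `Var(IC_j1(O_i) − IC_j2(O_i))` and estimates it by `(1/n) Σ (IC_j1(O_i) − IC_j2(O_i))²`.

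Step 12 of SAP A.5.4 covers the survey-augmented primary analysis. There the variance of the estimator of the arm mean E[Y(a)] "may be estimated with the sample variance of the efficient influence curve".

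SAP 4.2 sends the reader to the Supplement for variance estimation. Protocol 10.3.3 says only that influence function-based variance estimators will be used "to conduct Wald-style tests of the null hypotheses and to construct 95% confidence intervals". No other variance formula for the TMLE analyses appears in either document.

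**The concern.** An estimator with an influence curve behaves, in large samples, like the truth plus the average of the n individual influence-curve values. Its variance is therefore the variance of one value divided by n. A.4 gives the variance of one value and calls it the variance of the estimator; step 12 does the same for the arm mean.

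These two places are the only written variance rules behind:

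- the primary Wald tests at 3 and 6 months;
- the tests for Secondary objectives II and III;
- the confidence intervals of every TMLE comparison, including the descriptive Secondary I comparisons.

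The cost-effectiveness ratio uses a percentile bootstrap (SAP 4.4) and is not affected. Anyone who programs or reproduces the analysis from the SAP text as it stands would obtain unusable intervals and tests that cannot reject.

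**Working it through.** **Inputs from the plan.** n = 240 enrolled, with 20% loss expected by month 3, leaving 192; allocation 2/3 intervention and 1/3 SOC; SOC adherence about 27% at month 3; 5% censoring per interval in the power simulation (all Protocol 10.2.3). Tests are two-sided at 0.05 (Protocol 10.3.3).

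**1. The plan's own figure.** Protocol 10.2.3 states that "we may conclude that the study has >80% power to detect a six-month treatment effect of 20" percentage points even with no three-month effect, and the converse for month 3. The mechanism gives SOC adherence of logit⁻¹(−1) = 0.269 at month 3 and 0.269 × 0.5 + 0.731 × 0.182 = 0.268 at month 6. For a 20-point effect at month 3, 5% censoring leaves 76 SOC and 152 intervention participants:

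- Variance with division by n: 0.269 × 0.731/76 + 0.469 × 0.531/152 = 0.00423, so SE = 0.065 and z = 0.20/0.065 = 3.08. Approximate power is Φ(3.08 − 1.96) = 0.87.
- SE as written: 0.065 × √240 = 1.01, so z = 0.20.

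The mechanism was also simulated with 4,000 data sets per scenario and an arm-mean influence curve, because the simulated covariates are not predictive:

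| 20-point effect at | Power with division by n (two runs) | Power as written |
|---|---|---|
| Month 3 only | 0.85, 0.86 | 0.000 |
| Month 6 only | 0.83, 0.85 | 0.000 |

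With division by n, the mean month-3 SE (0.062 to 0.065) matched the empirical SD of the estimates (0.063 to 0.065), and the rejection rate with no effect was 0.050 to 0.057. A joint two-time-point test gave power of 83% and 81% with division by n, and zero without it. The protocol figure is therefore reproduced only with division by n.

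**2. The general factor.** SE as written / correct SE = √n: √240 = 15.5, or √192 = 13.9. The natural n is 240, because participants with a missing outcome still contribute to the influence curve.

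**3. Size on the risk-difference scale.** Assume an unadjusted influence curve, 1:2 allocation and a fraction o of outcomes observed. Then

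`Var(IC difference) = p0(1 − p0)/(o/3) + p1(1 − p1)/(2o/3)`

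With p0 = 0.27, p1 = 0.41 and o = 0.8: 0.1971 × 3.75 + 0.2419 × 1.875 = 1.193, SD 1.092, correct SE = √(1.193/240) = 0.0705. With o = 0.4 the variance is 2.385. The 40% is an assumption; SAP 6.2 says only that missingness in dried blood spots will be high.

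| Observed | Half-width as written | Half-width correct | z as written | z correct |
|---|---|---|---|---|
| 80% | 2.14 | 0.138 | 0.13 | 1.99 |
| 40% | 3.03 | 0.195 | 0.09 | 1.40 |

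A risk difference cannot leave the range −1 to 1.

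**4. Can the primary test reject as written?** At p0 = 0.27 the largest z occurs at p1 = 1: z = 0.73/√(0.1971 × 3/o). This is 0.85 at o = 0.8 and 0.95 with no missing data, both below 1.96. Rejection needs extreme rates: at p0 = 0.05 and o = 0.8, p1 must be at least 0.9755.

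**5. Step 12.** The A.5.3 curve contains no 1/n. It was coded without covariates, with a binary survey variable. The assumptions were adherence of 27% and 47%, blood-sample missingness of 20%, 40% and 60%, and survey missingness of 15%. The SE as written was 14.9 to 15.5 times the empirical SD; dividing the variance by n brought the SE to within about 4% of it.

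**The case against.** The strongest reply is that this is a notation slip. In A.4 the mean squared difference is a correct estimate of `σ_j²` as defined; what is wrong is calling `σ_j²` the variance of the estimator rather than of the √n-scaled estimator. Protocol 10.3.3 names the method, so the intended procedure is hardly in doubt. Taken literally, the formula gives intervals wider than the possible range, which would be obvious in the results table, and the error is conservative, so it cannot inflate type I error. SAP 6.1 lists the analysis as done on 20 April 2022 and the revision history dates the supplement rewrite to June 2022, so the text largely records completed work. The protocol's power simulation used longitudinal TMLE and does not cite A.4, so it is not a second statement of the same formula.

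Most of this stands, and it limits the point to the written formulas; nothing here shows that any reported result is wrong. It does not remove the omission. Protocol 10.3.3 does not print the factor. Reading the influence curve as already scaled by 1/n does not help either: A.5.3 shows an unscaled curve, and A.4's leading 1/n would then itself be wrong. The slip occurs twice, once as a formula and once in plain prose. The A.5 estimator also has its own estimand, influence curve and fluctuation steps, so its variance may well have been programmed from this text.

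**Conclusion.** The concern holds. As written, both variance rules give standard errors √n too large, 15.5 times at n = 240. That factor needs no assumption beyond n. The interval widths and z values also rest on the unadjusted curve, the 1:2 allocation and the stated observed fractions. Followed literally, the binary primary tests could not reject for any effect at the planned SOC rate of 27%. Because the protocol's power figure requires division by n, the likeliest explanation is an error of text rather than of analysis, but the documents do not show the code. These are the only stated variance rules for the primary tests and intervals, so they should be corrected.

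**What to change.** - **A.4:** state that the estimator of the difference is approximately normal with variance `σ_j²/n`, estimated by `(1/n²) Σ (IC_j1(O_i) − IC_j2(O_i))²`.
- **A.5.4, step 12:** say that the variance is the sample variance of the efficient influence curve divided by n. For the treatment difference, refer to the corrected A.4 rule: the sample variance of the difference between the two arms' curves, divided by n.
- **Code:** confirm that the executed analysis divides by n, in particular for the A.5 estimator.

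The cost is two lines of SAP text and one check of the code. If the code already divides by n, nothing needs re-analysis. If it does not, standard errors, confidence intervals and p-values must be recomputed; the point estimates do not change.
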